**SUMMARY**

Object of the investigation	Embozene TANDEM™ 100 µm microspheres
Full Title	Multicenter spanish observational, prospective study to evaluate the safety of transarterial Chemoembolisation (TACE) with tight calibrated and doxorubicin-releasing microspheres of 100 microns in the treatment of Hepatocellular Carcinoma (HCC)
Study Identifier	FJD-TAN-2014-01. Version 1.1, March 15 th , 2015
Study Description	Prospective Post-authorization study of follow-up (EPA-SP)
Promotor	[name], MD, PhD Vascular and Interventional Radiology Service Ramon y Cajal University Hospital. [name]. [contact] [contact]
Principal Investigator	[name], MD, PhD Vascular and Interventional Radiology Service Ramon y Cajal University Hospital. [name]. [contact] [contact]
Primary Objective	Safety and tolerability of DEB-TACE of non-resectable HCC, using 100-µm doxorubicin-loaded microspheres
Secondary Objectives	6-, 12- and 24-month local tumor response and 2-year Over All Survival
Number of Investigators	10 Spanish University Hospitals (See annexed II)
Number of participants	130
Inclusion Criteria	Confirmed diagnosis of HCC, Subject is competent and willing to provide written informed consent, Adults (male or female) patients ≥ 18 years of age, ECOG performance status is 0 – 1 or Child-Pugh classification is A, B7, Multinodular or single nodular tumor ≥3 – 9 cm, No invasion in the major blood vessels, Proper blood, liver, renal, heart function: testing result within 2 weeks of start, No current infections requiring antibiotic therapy, Not actively on anticoagulation drugs, Measureable disease per the modified Response Evaluation Criteria in Solid Tumors (mRECIST), Life expectancy ≥ 6 months
Exclusion Criteria	(ECOG performance status ≥2; or Child-Pugh class B8 or C, Bilirubin levels >3 mg/dl, HCC with large vessel or biliary duct invasion, diffuse HCC or extrahepatic spread, Patients in which any of the following are contraindicated or present (The use of doxorubicin, MRI or CT scans, Hepatic embolization procedures, WBC < 3000 cells/mm  , neutrophil < 1500 cells/mm  , Cardiac ejection fraction < 50 percent, Elevated creatinine greater than or equal to 2.5 mg/dl, Impaired

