### 3.2 Inclusion Criteria

1. Confirmed diagnosis of CHC according to EASL criteria and staged according to BCLC criteria
2. Patients with indication for TACE with 100 micron microspheres according to the usual practice of the center
3. Subjects in full power and willing to give their written informed consent to participate in the study.
4. Adult patients (men or women)  $\geq$  18 years of age.
5. Good quality of life. ECOG 0-1.
6. Child-Pugh preserved liver function  $\leq$  B7.
7. Absence of tumor invasion in the main Porta vein or main bile ducts
8. Possibility of undergoing diagnostic tests with CT or MRI.
9. Liver, cardiac and renal function, preserved, with these test results in two weeks from the registration of this study:
  - a. White blood cells count:  $> 2000 / \text{mm}^2$
  - b. Absolute neutrophil count:  $> 1000 / \text{mm}^3$
  - c. Quick Index  $> 50\%$
  - d. Platelets count  $> 5 \times 10^4 / \text{mm}^3$  and.
  - e. Serum bilirubin  $< 3.0 \text{ mg / dL}$
  - f. ASL, ALT 5 times within the normal range
  - g. Serum creatinine  $< 2 \text{ mg / dL}$
  - h. Hemoglobin  $> 9.0 \text{ g / dL}$
  - i. Non-unstable coronary disease or recent MI ( $< 4$  weeks)
10. Absence of concomitant infections that require antibiotic treatment.
11. Disease measurable by the modified criteria for evaluating the response in solid tumors (mRECIST 1.1).
12. Life expectancy greater than six months.

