#### **4.2 Follow-up**

After the first TACE procedure, the following evaluations will be carried out:

1. Clinical and analytical control 10-20 days after discharge according to usual practice: Clinical visit in which the general condition of the patient is assessed and will be asked whether or not he had Sd. Post-pay, its duration and intensity. Analytical including blood count, coagulation tests, basic biochemistry, transaminases and bilirubin. The study may be extended with more complete imaging or analytical tests if the physician considers it necessary.
2. Dynamic liver CT or MRI every 3 m for the first 6 months and then twice a year according to usual practice.
3. Clinical and laboratory review every 3 m the first 6 months and then twice a year as usual practice until the progression, death or loss of patient follow-up, with a maximum of 5 years.
  - a. Quality of life assessment (ECOG)
  - b. Laboratory assessment
  - c. Evaluation of safety and efficacy and assessment of retreatment if appropriate.

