### **5 TUMOR RESPONSE ASSESSMENT**

#### **5.1 Study Variables**

Related to the patient and the disease: age, gender, etiology of liver disease, diagnosis of HCC, previous nodules treated with surgery, ablation or TACE, Child-Pugh score, BCLC stage of the tumor, size, location and number of patients. nodules, segmental vascular

invasion of the portal vein, bilioenteric shunt or previous biliary prosthesis, carrier of porto-systemic shunt, relevant concomitant pathologies.

- Variables related to the primary objective:

**Post-embolization syndrome:** in an adverse effect of TACE that is defined as a picture of abdominal pain, fever  $<38.5^{\circ}\text{C}$ , and variable degree leukocytosis that appears 24 hours after the procedure and can last up to 10 days. It can be accompanied by nausea, vomiting and asthenia. It is related to tissue necrosis and is self-limited, its treatment is symptomatic. Its incidence is variable and linked to the volume of necrotic tissue.

**Early adverse events** derived from the procedure during the first 30 days:

1. Liver failure defined by ascitic decompensation with elevation of serum Br, jaundice and transaminases  $>x5$  and / or hepatic encephalopathy.
2. UGIB of peptic or varicose origin
3. Intense pain that requires continued iv medication
4. High fever that is not justified by Sd. post refund
5. Liver abscess
6. Coagulative portal thrombosis
7. Acute pancreatitis
8. Acute cholecystitis
9. Renal failure, elevation of serum Cr  $\times 2$  its baseline value.
10. Pleural effusion

**Late adverse events** arising from the procedure between the first 30 days and 6 months:

1. Intrahepatic bile duct injury defined by dilation of biliary radicals with cholestatic symptoms.

Additional therapies against cancer (sorafenib, radioembolisation, symptomatic treatment) will be documented for all patients every three months until death.

**Mortality** in the first 30 days after treatment

- Variables related to secondary objectives: the information will be obtained from imaging studies performed interchangeably with liver MR or CT using intravenous contrast and performing three-phase dynamic studies (arterial, portal and balance phase). Imaging studies will be evaluated according to RECIST 1.1 criteria.

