  - **Tumor response.** Devascularization pattern according to RECIST 1.1 criteria. Response to treatment: The response will be classified as objective response, (OR) complete (CR), partial (RP), stable disease (EE) and tumor progression (PT) (2, 31, 32)
  - **Overall Survival (OS)**
  - **Cause of Death:** Tumor progression, complications of liver disease or others.

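### The plan lets response be read on MR or CT without tying follow-up to the patient's baseline modality, so a CT-MR reading difference may enter the response category unseen

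*Combined protocol and SAP*

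**What the plan says.** The Summary gives the secondary objectives as "6-, 12- and 24-month local tumor response and 2-year Over All Survival". Section 5.1 says of these variables that "the information will be obtained from imaging studies performed interchangeably with liver MR or CT using intravenous contrast", and sets one acquisition standard for both modalities: "performing three-phase dynamic studies (arterial, portal and balance phase". On reading, it says "Imaging studies will be evaluated according to RECIST 1.1 criteria", and on the outcome, "The response will be classified as objective response, (OR) complete (CR), partial (RP), stable disease (EE) and tumor progression (PT".

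Section 4.2 schedules the scans as "Dynamic liver CT or MRI every 3 m for the first 6 months and then twice a year according to usual practice". The only related eligibility requirement in section 3.2 is "Possibility of undergoing diagnostic tests with CT or MRI", which fixes no modality at baseline.

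The patient and disease variables listed in 5.1 do not include the modality of each scan. Section 6.1 plans a column graph for tumour response, with no count of modality changes, no stratum and no sensitivity analysis. No central or paired reading is described.

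**The concern.** A response category is a statement about change between scans. If the two scans come from different instruments, the apparent change is the tumour change plus any difference in how the instruments show the lesion. Sections 1.2 (Secondary Objectives) and 5.1 describe the endpoint as a devascularization pattern, so it depends on how enhancement appears, and this is where the imaging method can matter. Because the outcome is categorical, a modest reading difference can move a patient between response, stable disease and progression.

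If a centre switches because a scan was equivocal, the added error is related to the outcome and need not average out. At stake is how the 6-, 12- and 24-month response distributions are interpreted. On the planned variables and tables, a reader could not tell how many patients were compared across modalities, or whether the results depend on them.

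**Working it through.** **Reading the passages together.** Section 5.1 makes MR and CT interchangeable. Section 4.2 offers either at each scan: months 3 and 6, then twice a year, so 12, 18 and 24. Section 3.2 asks only that CT or MRI be possible. No section requires follow-up on the baseline modality. A within-patient change is therefore permitted by silence. Contrast and three-phase acquisition are required for both modalities, which limits the difference but does not show that the two give the same reading.

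**The plan's only design figure.** Sections 3.4 and 6.2 give an accuracy of 1.71% for an event proportion of 1% with n = 130:

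1.96 × √(0.01 × 0.99 / 130) = 1.71%. It reproduces.

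That figure concerns adverse events and this point does not depend on it. The same formula gives a scale for response. At a proportion of 50%, 1.96 × √(0.5 × 0.5 / 130) = 8.6 points.

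**Possible size.** The documents give neither the share of patients who switch nor the CT-MR reading difference. Everything below is illustrative.

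1. *Patients affected.* Let s be the share who switch (assumed 10% to 50%) and m the share of those whose category moves (assumed 5% to 20%). The number misclassified is 130 × s × m.
   - Low: 130 × 0.10 × 0.05 = 0.7 patients (0.5%).
   - High: 130 × 0.50 × 0.20 = 13 patients (10%).

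   These are gross counts, before errors in opposite directions cancel.

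2. *A fixed reading difference.* The Summary gives a tumour size of 3 to 9 cm. An assumed 5 mm difference is 5/30 = 16.7% of a 30 mm lesion and 5/90 = 5.6% of a 90 mm lesion.

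3. *A random reading difference.* Assume category limits of −30% and +20% of diameter, a switch error with SD equal to 10%, 15% or 20% of diameter, and no error without a switch.

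| True change, as read after a switch | Formula | SD 10% | SD 15% | SD 20% |
|---|---|---|---|---|
| None, read as progression | P(Z > 0.20/SD) | 2.3% | 9.1% | 15.9% |
| 25% shrinkage, read as partial response | P(Z < −0.05/(0.75 × SD)) | 25% | 33% | 37% |
| 35% shrinkage, read as less than partial response | P(Z > 0.05/(0.65 × SD)) | 22% | 30% | 35% |

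Rows 2 and 3 are errors in opposite directions around the same limit. With equal numbers of both kinds of patient they largely cancel in the response rate. Row 1 has no such built-in counterpart.

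The table applies only to switched pairs. With 10% to 50% switching, row 1 becomes 0.10 × 2.3% = 0.2% up to 0.50 × 15.9% = 8.0% of patients with an unchanged tumour.

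4. *Allowing for ordinary reading error.* Readings on one modality also vary. If that SD is 10% (assumed), the total SD after a switch is √(0.10² + SD²), or 14.1%, 18.0% and 22.4%. For a true 25% shrinkage, the part due to switching is then about 7, 10 and 13 points, not 25, 33 and 37. For an unchanged tumour, progression rises from 2.3% to 7.9%, 13.4% and 18.6%, an increase of about 6, 11 and 16 points. This allowance shrinks the response figures but not the progression figures.

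**The case against.** **The text does not expressly allow a within-patient switch.** This stands. Section 5.1 does not name the unit and can be read as accepting either modality across centres. The supportable statement is that a switch is permitted because nothing forbids it.

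**A reader might infer that switches could never be traced.** The documents do not support that. Section 9.1 refers to an annexed data collection booklet whose fields are not available here, and section 8.4 provides for checking data against the clinical history, where the scan type may appear. What can be said is that 5.1 does not list modality and 6.1 does not use it.

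**RECIST 1.1 is adopted by reference and may govern the matter.** That cannot be checked from these documents. No such rule is written into the plan, and the one explicit statement on modality points towards interchangeability.

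**A reader might take the misclassification percentages as the expected distortion.** They are not. Every input is assumed, they apply only to switched pairs, part of the error would occur without a switch, and errors around the response limit partly cancel. The model also uses diameter, whereas the stated endpoint is a devascularization pattern.

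**A reader might infer that survival is affected, because false progression would end follow-up.** Section 4.2 does end clinical and laboratory review at progression. However, section 5.1 documents later anticancer therapy for all patients every three months until death, so the documents do not show that survival data would be lost.

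**A same-modality analysis may itself be selective.** This stands. If switches follow equivocal scans, restricting to same-modality pairs drops patients for a reason related to outcome. It can serve only as a sensitivity analysis.

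**Imaging follows usual practice.** Sections 4.2 and 8.5 rule out a rigid modality requirement or extra procedures. A preference that yields to usual practice, plus recording, fits within them.

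**Conclusion.** The point holds as a minor one. The plan permits baseline and follow-up scans on different modalities, and neither its listed variables nor its planned analysis separates a resulting reading difference from tumour change. This rests on the wording of 5.1, 4.2 and 6.1 and on no outside figure.

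The size is unknown and may be small. The illustrative 0.5% to 10% of patients misclassified depends wholly on the assumed switching and reclassification shares. Only its upper end is comparable with the 8.6-point half-width that sampling error alone gives a response rate near 50%. The effect is confined to a descriptive secondary endpoint in a single-cohort observational study. The primary safety objective and overall survival are not affected.

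**What to change.** **Section 5.1.** In place of interchangeable use, write: *MR or CT, using the same modality as the patient's baseline scan where usual practice allows.* Add the modality of every scan to the listed study variables.

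**Section 6.1.** Keep all patients in the main response analysis. Report the number of modality switches, and the reason for each, at 6, 12 and 24 months. Add a sensitivity table of response restricted to pairs of scans on the same modality, with a note that this restriction may be selective if switches follow equivocal scans.

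**Cost.** One data field, one extra table and slightly less scheduling freedom for centres. No scan is added, and a centre may still switch when its usual practice requires it.

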### 1.2 Secondary Objectives

- **Local tumor control** based on the pattern of devascularization according to RECIST 1.1 criteria (2). If a patient is referred to a liver transplant: local tumor control based on histological analysis
- **2 year overall survival (OS)**

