## 3 STUDY POPULATION

### 3.1 Target population

Patients with confirmed HCC and stage B according to the BCLC classification. Patients with a less advanced stage (BCLC stages 0 and A) but who are not candidates or expressly reject radical treatments with surgery or radiofrequency.

Three possible groups of patients are considered:

- A.- Patients unfit for surgery or liver transplantation due to tumor extension, age and / or comorbidities.
- B.- Patients not eligible for a liver transplant for exceeding the Milan criteria but with the possibility of experiencing a backward step to a previous stage (down stage) by TACE within these criteria
- C.- Patients eligible for a liver transplant on the waiting list: to prevent tumor progression while on the waiting list.

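### Tumour response is labelled RECIST 1.1 throughout, but the source cited for that label is the mRECIST paper, and nothing in the plan reconciles the two

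*Combined protocol and SAP*

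**What the plan says.** Section 1.2 (Secondary Objectives) makes local tumour control a secondary objective, "based on the pattern of devascularization according to RECIST 1.1 criteria (2", where the closing 2 is the reference number. It then adds an exception: "If a patient is referred to a liver transplant: local tumor control based on histological analysis".

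Section 5.1 repeats the rule twice. For imaging in general: "Imaging studies will be evaluated according to RECIST 1.1 criteria". For the response variable itself: "Devascularization pattern according to RECIST 1.1 criteria". The list of response classes ends with "stable disease (EE) and tumor progression (PT) (2, 31, 32", the last three numbers being references. The scans are CT or MR with contrast, "performing three-phase dynamic studies (arterial, portal and balance phase".

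In the reference list, reference 2 is titled as the modified RECIST (mRECIST) paper for hepatocellular carcinoma. The title of reference 31 covers RECIST, WHO and newer alternatives. The title of reference 32 concerns imaging of liver tumours after treatment and names no criterion.

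Measurability at entry is set by mRECIST in the Summary and by mRECIST 1.1 in section 3.2, criterion 11. Section 6.1 plans a column graph of tumour response and names no criterion.

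**The concern.** The name of the criterion and the source given for it point to different things. The documents themselves treat mRECIST as a modification: the title of reference 2 calls it modified RECIST, and section 3.2 refers to modified criteria. A site that takes the label at face value would read scans by RECIST 1.1. A site that looks up the citation in section 1.2 would open the mRECIST paper.

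At stake is the meaning of the response rates that the Summary schedules at 6, 12 and 24 months. Ten hospitals take part, section 4.2 leaves follow-up imaging to usual practice, and no central reading is described. The plan therefore contains nothing that would bring the two readings back together, and a reader of the results could not tell from it which criterion produced them.

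**Working it through.** The check is mainly a comparison of text. Set side by side:

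| Place | Function | Criterion named | Source cited |
|---|---|---|---|
| Summary, inclusion criteria | Measurability at entry | mRECIST | none |
| 1.2 Secondary Objectives | Response, as devascularization | RECIST 1.1 | 2 |
| 3.2, criterion 11 | Measurability at entry | mRECIST 1.1 | none |
| 5.1, imaging studies | Reading of scans | RECIST 1.1 | none |
| 5.1, tumour response | Response, as devascularization | RECIST 1.1 | 2, 31, 32 |
| 6.1 | Analysis of response | none | none |

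1. **Label.** All three statements about response say RECIST 1.1. There is no disagreement among them.
2. **Citation.** In section 1.2 the only source for that label is the mRECIST paper. This is the firm mismatch.
3. **Other sources.** The response classes in section 5.1 cite reference 2 again. To judge by their titles, references 31 and 32 do not settle the matter: one covers several criteria and the other names none.
4. **Entry labels.** Measurability at entry is a different function from response, so mRECIST there does not contradict RECIST 1.1 for response. The hybrid name mRECIST 1.1 is supporting evidence that the two names were run together.
5. **Tie-break.** The response classes are listed but not defined, and the analysis section names no criterion. Nothing else in the documents decides between label and citation.

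**What the point does not touch.** The only design figure in the plan is the precision in sections 3.4 and 6.2. With n = 130, an event proportion of 1% and a two-sided 95% asymptotic interval:

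1.96 × √(0.01 × 0.99 / 130) = 0.0171, or 1.71%

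This matches the stated figure. Its inputs are n, the confidence level and an assumed event proportion; no response criterion enters.

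**Size.** To compute the effect on the response rate one would need response rates under each criterion, or a rate of disagreement between them. The documents give neither, so no figure is offered.

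**The case against.** The strongest reply is that the rule is stated. Section 5.1 says in terms that imaging is read by RECIST 1.1, and every statement about response agrees. That stands: it would be wrong to say that the plan names no criterion. It does not dispose of the point, because the same label is tied in section 1.2 to a paper on a different criterion, and no text explains why.

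A second reply is that this is a slip of citation in a secondary, descriptive endpoint. That stands as to weight. It is still the stated rule for reading a named endpoint and not background text, so it should be corrected.

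A third reply is that the documents do not describe what either criterion measures. That also stands. The point therefore rests on label against citation, and not on any claim that RECIST 1.1 cannot capture devascularization.

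Three stronger readings are tempting, and the documents do not support them:

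- *That sites will in fact read differently.* The plan leaves room for this, but nothing shows that it happens.
- *That the shift in a pooled rate is limited to one centre's share*, for example 13/130 = 10.0 points if 130 patients are spread evenly over ten hospitals. This is not a bound. Section 2 sets a minimum of 5 patients per centre and no maximum: nine centres with 5 leave 130 − 45 = 85 in the tenth, and 85/130 = 65.4%. More than one centre could diverge, and if all sites followed an unintended criterion no centre share would limit the error.
- *That overall survival is affected*, because section 4.2 continues review "until the progression, death or loss of patient follow-up, with a maximum of 5 years". The documents do not say by which criterion progression is read for that purpose, so this cannot be concluded.

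**Conclusion.** The point holds as an unreconciled mismatch between a label and its citation. The devascularization endpoint is called RECIST 1.1 wherever response is described, its only source in section 1.2 is the mRECIST paper, and the entry criteria show the two names being merged. A reader cannot tell from the documents which criterion was meant.

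The effect on reported response rates is unknown and cannot be computed from the documents. The scope is one secondary endpoint shown descriptively; the primary safety objective and the sample-size statement do not depend on it. It should be fixed, but it does not put the study's main purpose at risk.

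The conclusion assumes only that the title of reference 2 describes its content. It does not cover patients referred for transplant, whose local control rests on histology and whose number is not given. Section 3.1 does make them an expected group: "Patients eligible for a liver transplant on the waiting list: to prevent tumor progression while on the waiting list".

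**What to change.** Name one response criterion, and make label, citation and endpoint wording agree in section 1.2 and in both places in section 5.1.

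- **If mRECIST is meant.** The devascularization wording, reference 2, the measurability criterion and the arterial-phase imaging together point this way. Replace RECIST 1.1 with mRECIST (reference 2) in all three places.
- **If RECIST 1.1 is meant.** Cite a RECIST 1.1 source in place of reference 2 in both section 1.2 and section 5.1, and reword the devascularization endpoint in both.

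In either case:

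- Replace the hybrid mRECIST 1.1 in section 3.2 with the single intended name, consistent with the Summary.
- Keep the histology rule for patients referred to transplant, and repeat it in section 5.1 as a stated exception. At present that section describes imaging only.

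Once the criterion and its source agree, the response categories are defined by reference, and reprinting the thresholds is optional.

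The cost is wording only, through the amendment route in section 9.3. Section 5.1 already specifies three-phase imaging, so no scan is added.
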